Neonatal health and improving neonatal mortality has become one of the top priorities globally. In Rwanda, hospital care has advanced significantly with the development of national neonatal care guidelines and widespread provider training. As advances in technology and resuscitation become more commonly available, many preterm, low birth weight and other high-risk infants are surviving the early neonatal period. However, upon discharge from the neonatal units, this at-risk population has little support for their health, nutrition and development in the community. To address this emerging need, Partners In Health in collaboration with the Ministry of Health and UNICEF, has created a pediatric developmental clinic (PDC) to follow the high-risk infants after discharge from hospitals and health centers. Prior to implementation, a community-based descriptive study assessing the baseline medical, nutritional and developmental needs of low-birth weight and preterm infants who are the target population of the pediatric development clinic was conducted (Baseline Phase One). Subsequently, after 1-2 years of implementation an evaluation of clinical, nutritional and developmental outcomes of children followed in PDC will be conducted in comparison with the baseline study outcomes (Post-PDC Phase Two). Ongoing research on PDC implementation will focus on research on patient and provider experiences, overall clinic processes, cost-effectiveness, expansion of the PDC model, decentralization to health centers, and longer term outcomes of children enrolled in the PDC to further help refine the PDC model (Post-PDC Phase Three).

Table of Contents

1. Background	5
2. Aims of the study:	6
3. Methods.....	8
3.1. Study description	8
3.2. Study design.....	8
3.3. Study sites	9
3.4. Study population	9
3.5. Selection of study population	10
3.5.1. Inclusion criteria	10
3.5.2. Exclusion and Stop Criteria	11
3.5.3 Sampling	11
3.5.4. Randomization	12
3.5.5. Proposed Intervention	12
3.5.6. Recruitment Methods.....	13
3.5.7. Subjects enrollment	14
3.6. Study Procedures	15
3.6.1. Procedures at enrollment and data collection.....	15
3.6.2. Outcomes, exposures, and confounders to be measured	18
3.6.3. Data Management.....	22
3.6.4. Analysis Plan	23
4. Study Limitations.....	26
5. Ethical Considerations	27
5.1. Risks and discomforts.....	27
5.2. Potential benefits.....	27
5.4. Informed consent	28
5. Ethical approval	29
6. Logistics	29
6.1. Distribution of responsibilities.....	29
6.2. Timeline	32
6.3. Budget	33
Acronyms	34
References	35
Appendix A: Household Data Collection Tools	37

Appendix B: New Tools Phase 3	38
Appendix C: CVs of New Investigators	39
Appendix D: Prior RNEC Approvals	40
Appendix E: Payment Receipt for August RNEC Review.....	41
Appendix F: Previously Approved Study Tools.....	42

1. Background

Early childhood from birth to 5 years of age is crucial for brain development (Sices, 2007). This period of growth for children is enhanced through adequate nutritional and developmental support. Furthermore, early intervention has been demonstrated to have significant impact on long-term outcomes (Childers et al, 2011). For example, early intervention has been associated with improved IQ in the first five years of life and has decreased behavioral problems (Nordhov et al, 2010), (Nordhov et al, 2012). Furthermore, studies have demonstrated that early intervention improves educational progression, incidence of delinquency and crime, and economic success (Baker-Henningham et al, 2010). Unsurprisingly, early childhood development support has been associated with improved outcomes of children in resource-limited settings as well (Ertem et al, 2008).

This critical time is especially important for high-risk populations, such as low- birth weight and preterm infants. Infants born premature or low birth weight are at increased risk for early death, developmental delay and nutritional and medical comorbidities (Feldman et al, 2006). Even infants born in the late preterm period, after 32 weeks up until 37 weeks, are at risk for adverse effects on development and academic difficulties (McGowan et al, 2011). Therefore, routine neurodevelopmental follow-up has increasingly become the standard of care in the United States and Europe for these infants (McManus et al, 2012).

In 2010 there were an estimated 15 million preterm (<37 weeks) births worldwide (Biencowe et al, 2013). It has been estimated that approximately 1 million of these infants have some degree of developmental delay. Some estimate that 200 million children in developing countries are not reaching their full developmental potential (Grantham-McGregor et al, 2007).

Improved quality of care can help reduce this burden. In Rwanda, up to 40% of under- five deaths occur within the first 28 days (Rwanda DHS 2010), and approximately 6% of all neonates born are low birth weight (WHO-ECDD 2012) with prematurity ranking among the top causes of under-five mortality (Rwanda Health Statistics, 2012). Currently, these infants are discharged from hospitals with little support out in the community.

To address this gap, Partners In Health, in close partnership with the Rwanda Ministry of Health and technical support from Boston Children's Hospital and UNICEF, is designing and implementing a Pediatric Development Clinic (PDC) specifically dedicated to the nutritional, medical and developmental concerns of this high-risk population, with the goal of improving the quality of life for affected infants and children. However, there is a lack of data regarding the current outcomes of these vulnerable newborns in resource-limited settings (Ballot et al, 2012).

The proposed study aims to assess the baseline needs and disease burden of low birth weight and preterm infants, whom will routinely be evaluated in this clinic and will comprise a large majority of the clinic patients. These data will be used to inform the development and implementation of a pediatric developmental clinic (PDC) to follow these infants long-term, with the goal of improving overall pediatric health especially for those high-risk children. Following 1-2 years of implementation, an evaluation of clinical, nutritional and developmental outcomes of children followed in PDC will be conducted in comparison with the baseline study outcomes. Additionally, the evaluation of PDC will continue after initial post-assessments focusing on research on patient and provider experiences, overall clinic processes, quality of care, cost of the PDC model, PDC training and mentorship, expansion of the PDC model, and longer term outcomes to further help refine the PDC model.

2. Aims of the study:

Phase One: Baseline/Pre-PDC

Aim 1: To describe the baseline outcomes of a selected sample of infants discharged from a rural hospital neonatal unit. This aim has been completed.

Aim 2: To identify specific patient-level predictors of developmental delay (if we have sufficient power based on prevalence of developmental delay in the sample population). This aim will not be completed due to the small sample size.

Phase Two: Post-PDC

Aim 3: To describe the pediatric development clinic (PDC) implementation process after approximately 24 months of implementation in terms of: services provided, referral system, patient population served and clinical, nutritional, and developmental status.

This aim has been completed.

Aim 4: To describe the clinical, nutritional, and developmental outcomes of vulnerable patients enrolled in PDC in comparison with:

- a) Medically vulnerable infants who did not receive PDC support from Phase One of this study. This comparison will be made using a cohort of preterm/LBW children who were born in Rwinkwavu District Hospital (RDH) before PDC started with medical, nutritional and developmental outcomes assessed at 12-36 months of age. under way
- b) The general population of rural Rwandan children. This comparison will be looking at developmental outcomes of children followed in PDC compared to the same age children from the general population using UNICEF data that was collected in under 5 children.¹

Phase Three: Expanding PDC

Aim 5: To evaluate the implementation of PDC during expansion, including patient characteristics, provider experiences, quality of care, impact of quality improvement interventions, cost-effectiveness, patient experiences, and patient outcomes. Findings from this aim will be used for continuous quality improvement of the PDC and informing scale-up.

Aim 5. 1. To evaluate the implementation of interventions that promote breastfeeding from as early as day one of life among newborns in the referring hospital neonatal units.

¹ The UNICEF data was conducted as part of an evaluation for UNICEF and Imbuto Foundation's ECD&F Baseline. PI of this study [name] and Co-I [name] were both on the UNICEF ECD&F study team and have access to the study data. The ECD&F study was approved by RNEC (PIs [name] and [name]).

3. Methods

3.1. Study description

This study has three phases. In the first phase, descriptive study will investigate at the community level the developmental, medical and nutritional outcomes of infants discharged from the neonatal unit, aged between 12 to 36 months at the time of data collection. In the second phase, the study will assess the services provided to children enrolled in the PDC and compare their outcomes to children from the first phase as well as to an existing random sample of children from an existing database. In the third phase, research will focus on answering questions raised from the initial PDC study aims – including patient and provider experiences, expansion of the PDC model, overall clinic processes, enrolment rates and retention, cost-effectiveness, and longer term outcomes of children enrolled in the PDC to further help refine the PDC model and maximize benefits for children.

3.2. Study design

Pre-PDC Phase One:

The first phase is a **cross-sectional study** of infants discharged from a district hospital unit using caregiver report of medical and developmental outcomes as well as relying on measured growth parameters for nutritional status. This study will serve as a baseline of developmental, medical, and nutritional outcomes for comparison to similar children who received services from the PDC.

Post-PDC Phase Two:

All under 5 years of age, high risk (preterm, LBW) children enrolled in PDC since April, 2014 when PDC was initiated. The second phase will be a second cross-section of children who have been receiving services from the PDC from April 2014 when the clinic launched until present. The study will describe PDC implementation, demographic characteristics, and clinical, nutritional and developmental outcomes of all children from zero to five years of age enrolled in PDC from April 2014 to the time of study.

Post-PDC Phase Three:

This phase will use mixed methods, with data sources including routinely collected data, chart review, household data collection, focus groups and interviews to evaluate the PDC as it expands to new areas. The study will provide essential information of the feasibility of the PDC model at larger scale. The study will describe barriers to care, retention, long-term patient outcomes, and provider and patient experiences, quality of care delivered in the PDC especially on growth monitoring and developmental screening and costing of the PDC.

3.3. Study sites

Pre-PDC Phase One:

Phase One data collection took place in the Rwinkwavu District Hospital catchment area: Nyamirama, Mukarange, Mwili, Murama, Rwinkwavu, Kabarondo, Ndego, Kabare, and Ruramira sectors.

Post-PDC Phase Two:

Phase Two data collection will take place in the PDC clinics in the Rwinkwavu District Hospital catchment area: Rwinkwavu, Kabarondo, Ndego, Cyarubare and Ruramira Health Centers. Additional data collection on patient outcomes will be collected during household interviews at the homes of PDC patients.

Expanding -PDC Phase Three:

Data collection will take place in all PDC clinics in the Rwinkwavu and Kirehe District Hospital catchment areas. Household data collection will be conducted in the communities of Kirehe District.

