3.5. Selection of study population

3.5.1. Inclusion criteria

Baseline Phase One:

All infants discharged from Rwinkwavu hospital neonatal unit and born at less than 37 weeks and infants born less than 2 kilograms during the designated study period.

Post-PDC Phase Two:

All children under five years of age enrolled in PDC in Rwinkwavu District Hospital catchment area PDC clinics, will be included in Aim 3 and Aim 4b. Aim 4a will include only preterm and/or LBW (<2000g) infants for comparison with the baseline population of similar infants.

Expanding-PDC Phase Three:

All children under five years of age and their caregivers referred to or enrolled in PDC in Rwinkwavu and Kirehe District Hospital catchment areas. In addition, newborns and their caregivers from Rwinkwavu and Kirehe District Hospital catchment areas will be included as the primary referral patient population to PDC. PDC providers will also be included in some components of the evaluation.

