3.5.2. Exclusion and Stop Criteria

Pre-PDC Phase One:

1. Any infant whose family is unwilling to consent to study or decides to stop the home visit at any time.
2. Congenital heart disease per neonatal register
3. Genetic dysmorphology per neonatal register
4. Birth asphyxia per neonatal register

Post-PDC Phase Two:

1. For Aim 4a, exclusion criteria will match the Baseline Phase One exclusion criteria listed above.

Expanding-PDC Phase Three:

1. Children who do not meet inclusion criteria will be excluded.

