3.6.4. Analysis Plan

Pre-PDC Phase One:

Aim 1: Describe the baseline outcomes of a selected sample of infants discharged from a rural hospital neonatal unit.

Analysis Plan:

The primary analysis will be a univariate analysis describing the proportion of children discharged from the neonatal unit with developmental delay at two years of age. This is the primary outcome of the study and will provide vital data regarding neonatal outcomes at two years after discharge from neonatal unit. Proportions will be calculated for categorical variables and means with standard deviations will be calculated for continuous variables.

Categorical variables include: sex, sector, alive/dead, malnutrition (yes/no), malnutrition category (low, moderate, severe), medical comorbidities (anemia, respiratory disease,

possible hydrocephalus, and feeding difficulty), ubudehe category (measure of economic status), and education level of the caregiver.

Continuous variables are birth weight, gestational age, age at the time of data collection, and household size.

Aim 2: Identify specific patient-level predictors of developmental delay

Analysis Plan:

We hypothesize that birth weight (< 1kg, 1-1.5kg, 1.5-<2kg, \geq 2 kg), gestational age (<32 weeks, 32-36 weeks, \geq 37 weeks), and malnutrition (yes/no) will be significantly associated with developmental delay in bivariate and multivariable analyses.

Chi square test will be performed to test for associations between these categorical variables and the primary outcome (developmental delay). A multivariable logistic regression model will be created to identify predictors of developmental delay controlling for potential covariates using the same list of descriptive variables. However, this analysis will only be performed if there are a sufficient number of children with the primary outcome to have sufficient power to detect predictors.

Post-PDC Phase Two:

Aim 3: Describe the PDC and patients enrolled in the PDC

Analysis Plan:

Demographic characteristics, services provided to patients, and clinical, nutritional and developmental outcomes will be described using descriptive statistics. For continuous variables, mean and standard deviations will be reported unless the distribution is not normal and then medians and inter-quartile range will be reported. Frequencies and percentages will be reported for categorical variables.

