Aim 4a: Compare developmental, medical, and nutritional outcomes of children who were enrolled in the PDC to medically vulnerable children who did not receive PDC support (from Baseline Phase One)

Analysis Plan:

We will use bivariate analyses to compare the outcomes of infants who received PDC services with those who did not receive these services (the baseline data from Phase One). Developmental delay will be scored as a binary outcome looking at the proportion of children who failed one or more ASQ-3 domain at baseline to the proportion of children enrolled in PDC who failed one or more ASQ-3 domain. We will use a chi square test or fishers exact test look for significant differences in the number of children with developmental delay between children who received PDC services and those who did not. Chi squared or fishers exact tests will also be used to assess for differences in nutritional outcomes (normal, moderate, and severe malnutrition indicators) and medical outcomes among the two groups.

If we have sufficient power, we will conduct logistic regression analyses to look at predictors of developmental delay in the sample. Using backwards selection, all variables associated with developmental delay at $p < 0.10$ in bivariate will be included in the full model. We will report Odds Ratio, p-value, and 95% confidence intervals for multivariate analyses.

Aim 4b: Compare developmental, medical, and nutritional outcomes of children who were enrolled in the PDC to a sample of Rwandan children from ten rural sectors across the country.

Analysis Plan:

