2. The high-risk infants who were hospitalized in the neonatal unit were not from one specific sector. The Rwinkwavu Neonatal unit serves as a referral center for the Southern Kayonza district. Each of the sectors within the district may not be environmentally identical. Specifically the availability of food, amount of rain and distance to health centers are factors that could influence the outcomes of the high-risk neonates and therefore could result in residual confounding.
3. The gestational age and birth weight are subject to misclassification.
4. This is cross sectional data, and therefore any associations found are unable to assess causality.
5. Exclusion criteria undiagnosed by register are subject to misclassification.

Post-PDC Phase Two:

1. This study will be a cross-sectional study, and therefore associations may be found, but we will be unable to assess causality.
2. For the Aim 4b comparing PDC participants and UNICEF sample, only similar age groups will be compared; therefore, the number of children may be reduced which might affect the power of the study and its external validity.
3. As this is a secondary dataset analysis, missing values are expected.
4. The gestational age and adjusted age are subject to misclassification due to recall bias.

Expanding-PDC Phase Three:

1. As this is primarily a secondary dataset analysis of routinely collected data, missing values are expected.

5. Ethical Considerations

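### Aim 4a should report a sector-adjusted comparison, because the baseline sectors and the PDC clinic sites overlap only in part and the planned test is unadjusted

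*Combined protocol and SAP*

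**What the plan says.** Section 3.3 (Study sites) gives the Phase One area as "Nyamirama, Mukarange, Mwili, Murama, Rwinkwavu, Kabarondo, Ndego, Kabare, and Ruramira sectors". For Phase Two it names PDC clinics at "Rwinkwavu, Kabarondo, Ndego, Cyarubare and Ruramira Health Centers" and adds: "Additional data collection on patient outcomes will be collected during household interviews at the homes of PDC patients". Both phases are placed in the Rwinkwavu District Hospital catchment.

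The Aim 4a groups are aligned on clinical features only. Section 3.5.1 states: "Aim 4a will include only preterm and/or LBW (<2000g) infants for comparison with the baseline population of similar infants". Section 3.5.2 states: "For Aim 4a, exclusion criteria will match the Baseline Phase One exclusion criteria listed above". Those exclusions concern consent and diagnoses, not residence.

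On sector, section 4 (Study Limitations, Phase One) warns that sectors might not share the same environment. It continues, "Specifically the availability of food, amount of rain and distance to health centers are factors that could influence the outcomes", and accepts that residual confounding could follow. The Phase Two limitations do not repeat this. Section 3.6.2 lists sector of residence as a potential confounder only for Aim 2, which section 2 says will not be completed.

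For Aim 4a, section 3.6.4 plans bivariate comparisons: "We will use a chi square test or fishers exact test look for significant differences". A logistic regression follows only if power allows. It looks for predictors of delay, selects variables by p < 0.10, and does not name sector.

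**The concern.** Baseline children were listed from the hospital neonatal register and visited at home, however far they lived from any clinic. PDC children reach the Aim 4 household interview only if they enrolled in the clinic programme at least 12 months earlier (sections 3.5.3 and 3.5.6). Distance to a clinic could reduce enrolment and retention in the PDC group, but it has no such filter on the baseline. If that happens, sectors without a clinic carry more weight in the baseline than in the PDC group.

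If delay or undernutrition also differs between the two kinds of sector, a crude comparison mixes that difference with any effect of PDC. The plan names the mechanism in its limitations but has no step in Aim 4a that would reveal or remove it.

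**Working it through.** **The plan's own figure.** There is none to reproduce. The documents give no sample size, power, delay rate or sector counts for Aim 4a.

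**Place lists (section 3.3).**
- Baseline: 9 sectors. PDC: 5 health centres.
- Names in both lists (4): Rwinkwavu, Kabarondo, Ndego, Ruramira.
- Baseline sectors with no clinic of the same name (5): Nyamirama, Mukarange, Mwili, Murama, Kabare.
- Health centre matching no listed sector (1): Cyarubare. If it lies in one of the five unmatched sectors, four remain without a clinic.

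**Illustration of size.** Let f0 and f1 be the shares of the baseline and PDC groups living in sectors without a clinic. Let d be the prevalence of delay in sectors without a clinic minus that in sectors with one. With no PDC effect:

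false difference = (f0 − f1) × d

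Assumptions, none of them in the documents: nine sectors of equal size, so f0 = 4/9 to 5/9; 40% delay in sectors with a clinic; equal groups of 120; two-sided 5% test. The 120 is borrowed from the incentives line of the Phase One budget (section 6.3) and is not a stated sample size.

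The rejection rate uses the normal approximation for two proportions, with pooled standard error under the null and both tails counted. Example with f0 = 5/9, f1 = 0, d = 10 points:
- Prevalences: 0.400 + 0.5556 × 0.10 = 0.4556 against 0.400, a difference of 0.0556.
- Pooled proportion 0.4278; null SE = √(0.4278 × 0.5722 × 2/120) = 0.0639; SE under these prevalences = 0.0638.
- Upper tail: Φ((0.0556 − 1.96 × 0.0639)/0.0638) = Φ(−1.09) ≈ 0.138. Lower tail ≈ 0.002. Total ≈ 0.14.

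| f1 | d (points) | False difference (points) | Rejection rate, 120 per group |
|---|---|---|---|
| 0 | 5 | 2.2–2.8 | 6–7% |
| 0 | 10 | 4.4–5.6 | 11–14% |
| 0 | 20 | 8.9–11.1 | 28–41% |
| 0.20 | 5 | 1.2–1.8 | 5–6% |
| 0.20 | 10 | 2.4–3.6 | 7–9% |
| 0.20 | 20 | 4.9–7.1 | 12–20% |
| = f0 | any | 0 | 5% |

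Ranges run from f0 = 4/9 to f0 = 5/9. A milder imbalance gives very little: f0 = 0.30, f1 = 0.20, d = 5 gives 0.10 × 5 = 0.5 points. A positive d favours PDC; a negative d reverses the sign.

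**Are the data available?** Section 3.5.3 extracts sector, cell, village and health centre for Phase One, and section 3.6.4 lists sector among the Aim 1 variables ("Categorical variables include: sex, sector, alive/dead"). Sections 3.5.3 and 3.5.6 extract household location for PDC patients. Sector can therefore be assigned in both groups.

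**The case against.** The strongest reply is that the two lists use different units. Sectors describe where baseline data were collected; health centres describe where clinics are held. Nine against five is not a comparison of where children live. A health centre may serve more than one sector, and section 3.5.5 admits referrals from the hospital, health centres and the community, so children from any sector can enrol. This stands. A reader might infer that the PDC group does lean towards clinic sectors; no sector counts, catchments or distances support that.

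A reader might also infer that the bias flatters PDC. The documents do not say which sectors are better off, and the limitation is hedged: sectors may differ, and the named factors could matter. Its distance is to health centres, not to PDC clinics. This stands too.

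The Phase Two limitations say that causality cannot be assessed. That tempers interpretation but does not show whether the groups differ by sector, nor remove the difference. Sector is also only one of several covariates left out of a historical comparison, so a pre-named covariate list including sector would largely meet the point.

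Finally, making a sector-restricted, sector-stratified comparison the main analysis would be hard to defend. Aim 2 was dropped for small sample size, and nine strata would leave sparse or one-sided cells. This also stands.

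**Conclusion.** The concern holds as a gap in the Aim 4a analysis, not as a demonstrated bias. The site lists make a difference in sector mix possible, the protocol's own limitations make it relevant, and the main analysis neither displays nor adjusts for it. The only multivariable step is conditional, data-driven and silent on sector.

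Direction and size are unknown. The illustrated range, from zero to about 11 points, rests wholly on assumed sector shares and prevalence gaps. The upper end needs a 20-point gap and no PDC child from a sector without a clinic, and nothing in the documents favours it. If the two groups have the same mix of the two sector types, this source of bias vanishes; a simple table would show whether they do. The stronger conclusions, that the groups come from different geographic frames or that the main comparison must be replaced, are not supported.

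**What to change.** In section 3.6.4, Aim 4a:

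1. State which sector Cyarubare Health Centre is in, and tabulate both groups by sector of residence.
2. Beside the crude comparison, report a pre-named sector-adjusted difference in developmental delay and in undernutrition, using Mantel-Haenszel risk differences with 95% confidence intervals. If strata are sparse, collapse to sectors with versus without a PDC clinic.
3. As a sensitivity analysis, repeat the comparison in sectors well represented in both groups, with that threshold set in advance.
4. Carry the sector limitation from Phase One into the Phase Two limitations.

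**Cost.** SAP wording, a little more analysis and some loss of precision; no new data. A stratum with children from only one group adds nothing to a Mantel-Haenszel estimate, so if few PDC children live outside clinic sectors, the adjusted result mainly describes clinic sectors and should say so. Collapsing to two strata leaves differences within each type unadjusted. Aim 4a is marked as under way, and the Phase Two timeline (section 6.2) ends in May 2016, before the September 2017 approval. If outcomes have already been compared, the adjusted analysis should be labelled as added afterwards.
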